5.30.2 Development of Hospital Trial Materials for Participating Units

The ABATE Infection Trial materials will be modeled after those developed for the REDUCE MRSA and Project CLEAR Trials. Here, we describe the materials that will be created in the planning year. The manner in which these materials will be used is described in detail in UH3 Aim 1 (see Section 6.10.8 and 6.10.9).

Study arm-specific binders will be developed for distribution after randomization (see Section 6.10.5). These will be distributed to each hospital’s leadership, infection prevention program liaisons, and the nurse educator, nurse manager, and medical director of participating units. We anticipate 50 hospitals with an average of 4 participating units each, for a total of 14 binders per hospital, or 700 total binders (350 per arm). Binder contents are detailed in **Table 3**. In addition to distributing paper copies of this binder by mail, we will also use HCA’s intranet (Atlas) to post these trial-specific materials. Similar to our prior trial, study arm-specific intranet sites will be created; each site will have access only to material about its assigned treatment regimen.

Table 3. Contents of ABATE Infection Trial Toolkit Binders

Educational Material	Description
1. Welcome and Summary of Goals	Introductory information on the trial
2. Study Investigators	Lists all investigators and collaborators involved in the trial
3. Table of Contents	Summary of documents included
4. Phone Matrix	Contact information for lead investigators, HCA co-investigators, and study staff
5. Frequently Asked Questions*	Answers to common staff questions about the trial or protocol
6. Patient Talking Points*	Talking points for common patient questions about the trial or protocol
7. Dos and Don'ts*	Quick reference guide on protocol
8. Kick-Off Protocol PowerPoint*	PowerPoint slides used in the kick-off webinar
9. Computer Based Training*	Printout of protocol training module
10. Just in Time Training*	On-the-spot training and reference guide for temporary/float nurses
11. Patient Instructions	Patient instruction sheets for self-bathing/showering with chlorhexidine
12. Nursing Protocol**	Nursing protocol for use of chlorhexidine and mupirocin
13. Study Related Events Form**	Forms for reporting study related adverse events
14. Technical Document*	Instructions on setting up nursing protocol and pharmacy orders

*Indicates arm specific information (control vs. intervention arm)

** Decolonization arm only

HCA routinely uses computer based training (CBT) modules to ensure completion of required health learning activities. The system (HealthStream) allows selective assignment to specific hospitals, units, and job types throughout HCA hospitals. We will develop arm-specific CBT modules to be completed by all frontline staff who work in participating units. The CBTs will focus on the rationale behind the trial, review protocol details related to the assigned treatment arm, and make clear that the assigned treatment is routine practice for the hospital for the duration of the trial. Compliance will be tracked locally and centrally by HCA’s Director of Clinical Education Development, who will provide detailed reports to HCA co-investigators.

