It is important that we not simply assume that approaches that work in ICUs will also work in non-ICU settings or have a beneficial effect on HAIs that manifest after discharge. There are several reasons for this. First, the decolonization regimen cannot be delivered in an identical fashion in the non-ICU setting. Patients are awake and some may refuse a daily bath. In contrast to the ICU, where bed baths are uniformly performed, patients may choose to perform their own bed bath. Others may choose to shower, where rinsing of the chlorhexidine leaves less residual effect on the skin compared to patients who receive a no-rinse bed bath. Thus, in the current delivery model, it will be more difficult to standardize the intervention or ensure that it is applied uniformly and effectively. Nevertheless, this is an important aspect of pragmatic clinical trials in non-ICU settings. Second, the level and intensity of contact differs between patients and nursing staff, and between patients themselves, especially those sharing a room. Since these interactions are important determinants of transmission of pathogens to patients, the results of an ICU intervention are not necessarily predictable in the non-ICU setting. Third, because the use of invasive devices is lower in non-ICU settings, reducing the density of bacterial reservoirs on the skin and in the nose may convey a smaller benefit. Finally, when applied to all patients in general hospital units, widespread use can incur meaningful incremental cost, small risks of skin rashes, the unpleasantness of intranasal application of ointment, and a risk of eliciting antimicrobial resistance. There are also potential opportunity costs of widespread adoption, since hospitals will need to be alert to concomitant use of other products that are not compatible with chlorhexidine bathing. Thus, it is important to test the effectiveness of a decolonization regimen under conditions of actual use, and to assess both its impact on infections, but also to monitor adverse effects on individuals and microbial resistance patterns.

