5.30.3 Development of Electronic Nursing Documentation Modules

HCA uses a centralized system (MEDITECH) for documentation of nursing care. We will create arm-specific electronic MEDITECH documentation screens that will require nurses to answer questions each daytime and evening shift about whether each of their patients was bathed with chlorhexidine and whether nasal mupirocin was administered. In the Usual Care Arm, if a chlorhexidine bath or shower was provided (non-compliance with protocol), it will require one of the following reasons (e.g. pre-operative bathing, physician order, or free-text response). In contrast, in the Decolonization Arm, if chlorhexidine is not given (non-compliance with protocol), it will similarly require one of a different set of reasons (e.g. patient allergic, patient refused, physician refused, or free-text response). An example from our prior trial is found in **Appendix C**. These responses will be tracked for monthly compliance assessments in both arms.

5.30.4 Development of Laboratory Materials for Collecting Bacterial Isolates and Launch of Baseline Strain Collection

In the planning year, we will also develop materials for the microbiology laboratories of participating hospitals to begin to collect bacterial strains throughout the trial. The reason for collection is to assess whether universal decolonization engenders resistance to decolonizing agents. Requested strains will include MRSA as well as select gram negative bacteria in which resistance to chlorhexidine has been reported. Laboratories will collect, batch, and send bacterial isolates on a monthly basis using the same protocol regardless of arm. Full details are provided in UH3 Aim 2, but the development of materials is described here.

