5.40.2 Hospital Corporation of America Centralized Data Warehouse

The following data elements (Table 4) will be requested from HCA’s Information Technology team to sample patient descriptors and baseline primary outcomes and ensure adequate processes for high quality data pulls. For details about trial design, outcomes, and analysis, see UH3 Aim 1 (Section 6.10).

Table 4. Data Elements Requested from HCA’s Centralized Data Warehouse

Source Data	Desired Results	Elements
Primary Outcome		
Census Data	Adult patient days by unit Readmissions within 30 days	Patient identifier (coded), hospital, unit location, hospital and unit admission date, hospital and unit discharge date, age in years, gender
Microbiology Finalized Results	Sterile site cultures, all pathogens	Pathogen name (if culture is positive), patient identifier (coded), date of collection, body site of collection, antimicrobial susceptibility, quantification of urine culture count (e.g. >50,000 colonies)
Claims data	Identification of infectious readmissions	Diagnosis codes (ICD9) Procedure codes (ICD9/CPT codes)
Descriptors		
Claims data	Identification of comorbidities Use as case mix adjustors	Diagnosis codes (ICD9)
Pharmacy	Mupirocin dispensing	Patient identifier (coded), date range dispensed, unit location
Supply Chain	Chlorhexidine use	Patient identifier (coded), date used, unit location

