6.10.52 Communication Infrastructure to Hospitals and Laboratories

We have a robust communication infrastructure to participating hospitals and laboratories (**Table 9**).

Table 9. ABATE Infection Trial Communication Infrastructure

Communication Component	Purpose
Toll-Free Number	ABATE Help Line for participating hospitals and units
Email Account	ABATE email for participating hospitals and units
Electronic Surveys	Method for obtaining standardized information from participants. To date, 4 surveys have been conducted (enrollment, facility details, unit details, unit engagement)
Coaching Calls	Webinar-based power point presentations detailing progress, upcoming activities, and timeline. Also used to feedback compliance to participants. Occasionally used for relevant special expert presentations (cutting edge science). System logs user and time on/off call. During intervention phase, coaching calls will be arm-specific and occur once monthly for the routine care arm and twice monthly for the intervention arm.
Polling Questions	Electronic webinar-based polling questions that detail respondent and answer for rapid, real-time inquiries during coaching calls
Toolkits	Binders distributed to each unit and hospital trial leaders with introduction, trial phone numbers/contacts, protocols, staff training materials, patient education materials, frequently asked questions, wall posters/clings.
Podcasts	Brief audio files (~3 min) recorded by trial investigators covering topics raised by participating hospitals. Intended for use by hospital educators for front line staff to address concerns, misconceptions, and important processes.
Video	Brief video for bathing training intended for front line staff by educators, managers
Observation Forms	Standardized assessment forms for direct observation of adequacy of bathing process; used as one method for determining compliance which is feedback to participants
Study-Related Event Form	Form to report potential study-related events
On-Site Training	In-person train-the-trainer sessions on application of bathing cloths

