In addressing considerations of interim analyses to determine whether early stopping might be possible, the decision has been made not to pursue an interim analysis for several reasons. First, this trial meets the requirements of a minimal risk study. The study of topical bathing/decolonization therapy necessitates neither interim analyses nor stopping rules since reasonably anticipated adverse events are considered minor. Second, the collection time plus the lag in obtaining data and the relatively sparse power suggest that it is highly unlikely that an early look would result in a stoppage of the trial for either futility or success. Third, the addition of an interim analysis would affect power estimates in such a way to create an elongation of the trial beyond the time period that is acceptable to our health system partner. As described in detail above, participation in the trial requires a continuous assertion that other hospital interventions and campaigns that may conflict with the trial will not be pursued. This restriction to the usual tendency of hospitals to pursue multiple simultaneous interventions for prolonged periods of time was a critical consideration in designing the length and size of this trial. With regard to assessment of adverse events, we have built in a reporting system for both mild and severe side effects, defining study-related events that show no signs of improvement within 7 days of stopping product as serious events. The study-related events monitoring and reporting system is described in detail in our Data Safety Monitoring Plan and in our Decolonization Educational Materials.

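### The adverse-event form is issued to the decolonization arm only, and the supplied protocol and SAP specify no between-arm comparison of skin or allergic harm

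*Protocol*

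**What the plan says.** Protocol 5.30.2, Table 3, item 13 is the study-related events form, described as "Forms for reporting study related adverse events". Its footnote reads "Decolonization arm only". The intranet copies do not widen access, because "each site will have access only to material about its assigned treatment regimen".

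Protocol 6.10.52, Table 9 lists the same item as "Form to report potential study-related events", with no arm stated.

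Protocol 6.10.11 describes the reporting system as "defining study-related events that show no signs of improvement within 7 days of stopping product as serious events". It refers the detail to the Data Safety Monitoring Plan and the decolonization educational materials. SAP 2.2 makes the same reference without the definition.

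Protocol 5.30.3 gives allergy as an example reason in the Decolonization Arm. If chlorhexidine is not given there, "it will similarly require one of a different set of reasons (e.g. patient allergic, patient refused, physician refused, or free-text response". The Usual Care Arm has its own reasons, which explain why chlorhexidine was used.

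On intent, Protocol 1.4 mentions a small risk of rash and says it is important "to monitor adverse effects on individuals and microbial resistance patterns". Sections 2.1 and 4.1 (the fourth element of comparative effectiveness research) speak of measuring both benefits and harms. The one harm then named is differential resistance.

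Protocol Table 10 (6.10.6) and SAP Table 1 (2.1) contain resistance but no harm of the skin or allergic kind.

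**The concern.** A count of events from one arm has no comparator. Rashes can also occur with ordinary soap, and some usual-care patients may receive chlorhexidine before surgery or on a physician's order (5.10.3, 5.30.3). A usual-care nurse who sees a rash has no form in the binder. The decolonization arm depends on unblinded staff choosing to report. Such a count can neither show that skin or allergic harm is increased nor exclude a given increase, and under-reporting cannot be seen from it.

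The abstract says the trial should inform practice for 40 million inpatients a year. For an intervention given to nearly every patient, a low-frequency harm is part of that decision. Resistance receives a between-arm, between-period test (6.20.4). Individual tolerability receives none in the supplied documents.

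**Working it through.** **What the documents allow.** They give no rate, power or precision for skin or allergic events, so there is no figure to reproduce. Setting the sources side by side:

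- **Events form:** decolonization arm only (Table 3). Usual care has no numerator.
- **Serious-event definition:** depends on stopping study product (6.10.11). It has no usual-care counterpart.
- **Allergy reason in the nursing query:** listed for the Decolonization Arm only (5.30.3), and used for compliance. It has no usual-care counterpart.
- **Diagnosis codes:** held for each admission (5.0.3) and requested in Table 4 (5.40.2) for case mix and infectious readmissions. The cohort covers all participating hospitals, so they exist for both arms.

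Only the last could support a comparison, and none is specified. Table 4 lists no onset date for a diagnosis.

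**What a coded comparison could detect.** These figures are illustrative. Inputs from the documents are 400,000 patients (the abstract says over 400,000), 54 hospitals, a 12-month baseline and a 21-month intervention. Assumptions are that the 400,000 cover both periods in proportion to time, that arms are equal (27 hospitals each), and that the coded rate p is 0.2%, 0.5% or 1% of stays, taking one stay per patient.

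Patients per arm:

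- baseline: 400,000 × 12/33 ÷ 2 = 72,727
- intervention: 400,000 × 21/33 ÷ 2 = 127,273

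The variance of the log ratio of ratios, from the four arm-period counts, is V = 2/(72,727p) + 2/(127,273p). If each hospital's log rate also drifts between periods with standard deviation s, add 2s²/27. The detectable ratio is exp(2.8√V), for 80% power at two-sided 0.05.

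| p | V, s = 0 | s = 0 | s = 0.25 | s = 0.5 |
|---|---|---|---|---|
| 0.2% | 0.02161 | 1.51 | 1.57 | 1.75 |
| 0.5% | 0.00864 | 1.30 | 1.38 | 1.59 |
| 1% | 0.00432 | 1.20 | 1.30 | 1.53 |

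The drift term is 2 × 0.0625/27 = 0.00463 for s = 0.25 and 2 × 0.25/27 = 0.01852 for s = 0.5. For example, at 1% with s = 0.5, V = 0.00432 + 0.01852 = 0.02284, √V = 0.151, and exp(2.8 × 0.151) = 1.53.

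A cruder check uses the intervention period only, with 27 hospitals per arm, about 4,714 patients per hospital (400,000 × 21/33 ÷ 54) and a between-hospital coefficient of variation of 0 to 0.5. It gives ratios from 1.12 to 1.51 at 1%, and up to 1.83 at 0.05%.

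**The case against.** The strongest reply is that Table 3 lists binder contents and is not the safety plan. The detailed description is said to be in the Data Safety Monitoring Plan, which was not supplied. Table 6 (5.60.0) and Table 9 mention the forms without an arm limit. This stands in part. A reader might infer that usual-care events are not collected at all, or that harms cannot be compared; the documents support neither. Table 9 does not contradict Table 3, however: it also leaves on-site cloth training without an arm label, although Table 15 (6.50) gives that training to decolonization hospitals.

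A second reply is that this is a reasoned choice. The form concerns study-related events, and usual care is assigned no study product. The agents have a long safety record (1.10), and anticipated events are considered minor (6.10.11). Section 1.4 says monitor, not compare. It would therefore be too strong to infer that the protocol promised a between-arm test of rash and dropped it. But in 6.10.11 the minimal-risk argument justifies having no interim analysis or stopping rules; it does not address the missing comparator.

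A third reply concerns the codes. It is tempting to say that they miss mild rashes equally in both arms. In an unblinded trial (6.10.13), decolonization staff have forms, training and an allergy prompt, so charting and coding may rise in that arm after baseline. The arm-by-period contrast would not remove this. A 30% relative rise in coding alone would give a ratio of 1.30, equal to the detectable ratio at 0.5% without drift. This stands, and limits the coded outcome to an exploratory role.

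Nor does the allergy entry in the nursing query supply a comparator. It is listed for one arm only.

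**Conclusion.** The point holds in limited form. In the supplied documents, adverse events are reported on a form issued to one arm, and no between-arm comparison of skin or allergic harm is specified, although the protocol says it will monitor adverse effects on individuals and measure harms. Collection in usual care under the Data Safety Monitoring Plan remains possible and should be confirmed.

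The codes could give an informative, imperfect comparison. The detectable ratio is about 1.2 to 1.5 for assumed coded rates of 1% down to 0.2% without hospital drift, and about 1.3 or 1.5 at 1% with an assumed drift SD of 0.25 or 0.5. Event rates, drift and the 12:21 split are all assumptions; the abstract does not say which periods its patient total covers. The primary and listed secondary analyses are unaffected.

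**What to change.** 1. Add an exploratory safety outcome to Protocol Table 10 and SAP Table 1: stays with any of a pre-listed set of ICD-9 codes for contact dermatitis, urticaria, allergic reaction or anaphylaxis, in both arms and both periods. Fix the list before any arm-level counts are seen.
2. Analyse it by arm, period and their interaction, with hospital clustering. The mixed logistic model of 6.20.4 suits this better than the proportional hazards model, because the listed data elements give no onset date. Report the interaction with a confidence interval.
3. State the limits alongside the result: mild rashes are probably often uncoded, reactions present on admission cannot be separated, and unblinded staff may code more rashes in the decolonization arm.
4. State in the protocol whether the Data Safety Monitoring Plan collects events in usual care, and make Tables 3 and 9 agree on which arms receive the form.
5. Reconcile allergy entries in the decolonization arm's nursing query with the forms received, only as a check on under-reporting in that arm.

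The cost is a code list, one further analysis of data already requested, a reconciliation, and short edits to the text. Section 6.10.4 says complete baseline data can still be obtained after the trial, so the coded outcome can be added with the intervention under way.

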5.30.3 Development of Electronic Nursing Documentation Modules

HCA uses a centralized system (MEDITECH) for documentation of nursing care. We will create arm-specific electronic MEDITECH documentation screens that will require nurses to answer questions each daytime and evening shift about whether each of their patients was bathed with chlorhexidine and whether nasal mupirocin was administered. In the Usual Care Arm, if a chlorhexidine bath or shower was provided (non-compliance with protocol), it will require one of the following reasons (e.g. pre-operative bathing, physician order, or free-text response). In contrast, in the Decolonization Arm, if chlorhexidine is not given (non-compliance with protocol), it will similarly require one of a different set of reasons (e.g. patient allergic, patient refused, physician refused, or free-text response). An example from our prior trial is found in **Appendix C**. These responses will be tracked for monthly compliance assessments in both arms.

5.30.4 Development of Laboratory Materials for Collecting Bacterial Isolates and Launch of Baseline Strain Collection

In the planning year, we will also develop materials for the microbiology laboratories of participating hospitals to begin to collect bacterial strains throughout the trial. The reason for collection is to assess whether universal decolonization engenders resistance to decolonizing agents. Requested strains will include MRSA as well as select gram negative bacteria in which resistance to chlorhexidine has been reported. Laboratories will collect, batch, and send bacterial isolates on a monthly basis using the same protocol regardless of arm. Full details are provided in UH3 Aim 2, but the development of materials is described here.

We will create a PowerPoint presentation for an introductory webinar to participating laboratories at the beginning of strain collection. This presentation will introduce laboratory staff to study staff and detail the entire process for de-identified strain collection. This will be followed by mailed laboratory toolkits (see example from prior trial, **Appendix E**), which will include 1) a Step-by-Step instruction sheet, 2) a Frequently Asked Questions (FAQ) sheet, 3) collection log sheets with a clipboard, 4) de-identified study ID labels, 5) FedEx mailing instruction sheets, 6) a shipment packing list, 7) a shipping schedule, and 8) a quick reference wall chart with a streamlined diagram of key elements for collection (see example from prior trial, **Appendix F**).

In order to ensure that the volume of MRSA+ and gram-negative rod (GNR) isolates that are collected during the baseline period are sufficient to support analysis around whether or not study agents engendered resistance, it will be crucial to obtain a full 12-months worth of isolates. It is anticipated that participating ABATE Infection Study hospital laboratories will begin collecting and banking isolates that fit study criteria beginning 3/01/2013 and continue collection through 2/28/2014 in order to support this activity. Collected isolates will include MRSA+ and the following eight select GNR organisms. Isolates will have already been collected as part of a patient's routine medical care.

E. coli	P. aeruginosa
K. pneumoniae, K. oxytoca	A. baumannii
P. mirabilis	S. maltophilia
S. marcescens	Burkholderia spp.

Once full IRB approval is obtained (either via ceding to the HPHC IRB or pursuing individual review) at each participating hospital during the baseline year (see Section 5.20.0), isolates may then be shipped to the central study laboratory at Rush University, Chicago for analysis and storage.

